### Table 14.2.5.1 Post-hoc Analysis: Clinical Status [0 - 2] in 11-point WHO Clinical Progression Scale (Full Analysis Set)

11-point WHO Clinical Progression Scale	Plitidepsin 2.5mg (N=XXX) n (%)	Plitidepsin 1.5mg (N=XXX) n (%)	Control Arm (N=XXX) n (%)
Clinical Status [0 - 2] at Day 4	xxx (xx.x)	xxx (xx.x)	xxx (xx.x)
Clinical Status [0 - 2] at Day 8	xxx (xx.x)	xxx (xx.x)	xxx (xx.x)
Clinical Status [0 - 2] at Day 15	xxx (xx.x)	xxx (xx.x)	xxx (xx.x)
Clinical Status [0 - 2] at Day 31	xxx (xx.x)	xxx (xx.x)	xxx (xx.x)

N = number of patients in analysis set; n = number of patients in each category; % = percentages are calculated based on N as the denominator.

Notes: 11-point WHO Clinical Progression Scale, where 0= uninfected, no viral RNA detected; 1 = asymptomatic, viral RNA detected; 2 = symptomatic, independent; 3 = symptomatic, assistance needed; 4 = hospitalised, no oxygen therapy (if hospitalised for isolation only, record status as for ambulatory patient); 5 = hospitalised, oxygen by mask or nasal prongs; 6 = hospitalised, oxygen by NIV or high flow; 7 = intubation and mechanical ventilation, pO2/FIO2  $\geq$ 150 or SpO2/FIO2  $\geq$ 200; 8 = mechanical ventilation, pO2/FIO2 <150 (SpO2/FIO2 <200) or vasopressors; 9 = mechanical ventilation, pO2/FIO2 <150 and vasopressors, dialysis or ECMO; 10 = dead.

If the 11-point WHO scale at Discharge is assessed on the same date as the Day 8 visit, the 11-point WHO scale assessment at Discharge is used.

Otherwise, if an unscheduled assessment is also collected on the same date of the Day 8 visit, the worst 11-point WHO score is used. Reference: Listing 16.2.6.1

Programming notes (not part of the table):

• Table template TEF009A.

• The displayed xxx do not reflect actual decimal precision. Please follow Section 2.11 for rounding rules.

#### Table 14.2.5.2 Post-hoc Analysis: Time to Initiation with Immune-modulating Drugs (Intent-To-Treat Population)

Variable Statistic	Plitidepsin 2.5mg (N=XXX)	Plitidepsin 1.5mg (N=XXX)	Control Arm (N=XXX)	
Patients who were Treated with Immune-modulating Drugs, n (%)	xxx (xx.x)	xxx (xx.x)	xxx (xx.x)	
Time to initiation with immune-modulating drugs (days) [a]				
n	XXX	XXX	XXX	
Mean (SD)	xx.x (xx.xx)	xx.x (xx.xx)	xx.x (xx.xx)	
Median	XX.X	XX.X	XX.X	
Q1, Q3	XX.X, XX.X	XX.X, XX.X	XX.X, XX.X	
Min, Max	XX, XX	XX, XX	xx, xx	

N = number of patients in analysis set; n = number of patients in each category or with data available; % = percentages are calculated based on N as the denominator.

SD = Standard deviation; Q1 =25th percentile; Q3 = 75th percentile; Min = Minimum; Max = Maximum.

[a] Time to initiation with immune-modulating drugs (days) = (first day on which a patient receives subsequent immune-modulating drugs – date of randomisation). Reference: Listing 16.2.4.7

Programming notes (not part of the table):

- Table template TEF009A.
- The displayed xxx do not reflect actual decimal precision. Please follow Section 2.11 for rounding rules.

#### Table 14.3.1.1.1 Post-hoc Analysis: Summary of Corticoid Therapy (As Treated Population)

Plitidepsin 2.5mg (N=XXX)	Plitidepsin 1.5mg (N=XXX)	Control Arm (N=XXX)
XXX	XXX	XXX
XX.X (XX.XX)	XX.X (XX.XX)	XX.X (XX.XX)
XX.X	XX.X	XX.X
XX.X, XX.X	XX.X, XX.X	XX.X, XX.X
XX, XX	XX, XX	XX, XX
xxx (xx.x)	xxx (xx.x)	xxx (xx.x)
XXX (XX.X)	XXX (XX.X)	xxx (xx.x)
xxx (xx.x)	xxx (xx.x)	xxx (xx.x)
XXX	XXX	XXX
xx.x (xx.xx)	xx.x (xx.xx)	xx.x (xx.xx)
XX.X	XX.X	XX.X
XX.X, XX.X	XX.X, XX.X	XX.X, XX.X
xx, xx	xx, xx	xx, xx
xxx (xx.x)	XXX (XX.X)	XXX (XX.X)
xxx (xx.x)	xxx (xx.x)	xxx (xx.x)
	Plitidepsin 2.5mg (N=XXX) XXX XX.X (XX.XX) XX.X XX.X (XX.X) XXX (XX.X)	Plitidepsin 2.5mg (N=XXX)Plitidepsin 1.5mg (N=XXX)XXXXXXXXXXXXXX.XXXXXX.XXX.XXX.XXX.XXX.XXX.XXX.XXX.XXX.XXX.XXXXXX.XXX

N = number of patients in analysis set; n = number of patients in each category or with data available; % = percentages are calculated based on N as the denominator.

SD = Standard deviation; Q1 =25th percentile; Q3 = 75th percentile; Min = Minimum; Max = Maximum.

[a] in dexamethasone base equivalents.

Reference: Listing 16.2.4.5 and 16.2.5.2

Programming notes (not part of the table):

• Table template TEF009A.

• The displayed xxx do not reflect actual decimal precision. Please follow Section 2.11 for rounding rules.

The below tables are a repeat of table 14.3.1.1.1 Post-hoc:

# Table 14.3.1.1.2 Post-hoc Analysis: Summary of Corticoid Therapy - Patients who did not Achieve a Sustained Withdrawal of Oxygen Supplementation (As Treated Population)

• Include only patients who did not achieve a sustained withdrawal of oxygen supplementation.

### Table 14.3.1.1.3 Post-hoc Analysis: Summary of Corticoid Therapy - Patients who Achieved a Sustained Withdrawal of Oxygen Supplementation (As Treated Population)

• Include only patients who achieved a sustained withdrawal of oxygen supplementation.

### Table 14.3.1.1.4 Post-hoc Analysis: Summary of Corticoid Therapy - Patients from Site ES40 (As Treated Population)

• *Include only patients from site ES40.* 

### Table 14.3.1.1.5 Post-hoc Analysis: Summary of Corticoid Therapy - All Patients Except Those from Site ES40 (As Treated Population)

The below listing is a repeat of listing 16.2.7.1:

#### Listing 16.2.7.5 Post-hoc Analysis: Adverse Events Considered as Nosocomial Infections Using the Wider Definition (Full Analysis Set)

Treatment Group: << Plitidepsin 2.5mg/Plitidepsin 1.5mg/Control Arm>>

Site ID - Patient ID	Age/Sex/Race [a]	Nosocomial Infection Type/ System Organ Class/ Grouped Preferred Term/ Verbatim	Start Date (Day)/ Stop Date (Day) [b]/ Duration (Days) or Ongoing	TEAE [c]	Severity/ Seriousness criteria	Relationship to Study Treatment	Action taken to Plitidepsin/ Dexamethasone/ Antiviral Control Arm [d]	Outcome
XXXX-YYYYY	XX/X/X	xxxxxxxxxxxxx/ xxxxxxxxxxxx/ xxxxxxxxxx	DDMMMYYYY (XX)/ DDMMMYYYY (XX)/ XX		Grade X/ xxxxxx	****	xxxxxxxxxxxxxxxxx/ xxxxxxxxxxxxxxx/ xxxxxx	XXXXXXXXXXX
123-456789 etc.	45/M/W	Musculoskeletal and connective tissue disorders/ Periarthritis/ Shoulder Periarthritis(Both)	14AUG2018 (82)/ 24AUG2018 (61)/ 15	*	Grade 5/ Death	No - Study disease	Not Applicable/ Dose not Changed/ Dose not Changed	Fatal

Note: The wider definition also considers AEs with SOC term 'Infections and infestations' that are discussed with the medical monitor and defined according to Centers for Disease Control and Prevention's health care associated infection definition (Horan TC et al).

[a] For sex, F = Female; M = Male. For race, AI = American Indian or Alaska native; A = Asian; BA = Black or African American; PI = Native Hawaiian or Other Pacific Islander; W = White; O = Other; UN = Unknown.

[b] Relative day to the start date of study treatment.

[c] TEAE=Treatment Emergent Adverse Event. TEAEs are flagged with \*.

[d] Antiviral control arm is the regulatory-approved antiviral for those patients randomised to the control arm, i.e., remdesivir or favipiravir.

MedDRA version & meddra.

Programming notes (not part of the listing):

- Listing template LAE001.
- Order by Site ID Patient ID and AE No.
- Assign the version of MedDRA Dictionary to & meddra. macro variable as XX.X and update the version of MedDRA Dictionary used for coding as needed.
- Nosocomial Infections using the wider definition are those AEs with ADAE.NOSOCOFL = Y.
- Nosocomial Infection Type is the "Column C" from the "Neptuno\_Nosocomial Infections\_13March2023\_updated by IM\_25Apr2023\_final.xlsx" file, and it must be presented as
  - $\circ$  Bloodstream Infection (for Column C = BSI)
  - $\circ$  Eye, Ear, Nose, Throat, or Mouth Infection (for Column C = EENT)
  - Lower Respiratory Tract Infection, Other than Pneumonia (for Column C = LRI)

Statistical Analysis Plan Addendum and TFL Mock Shells Fortrea Study: 000000213894 Protocol Reference: APL-D-003-20

- $\circ$  Pneumonia (for Column C = PNEU)
- Skin and Soft Tissue Infection (for Column C = SST)
- Urinary Tract Infection (for Column C = UTI)
The below figures are a repeat of figure 14.2.1.1:

# Figure 14.2.1.1.1 Post-hoc Analysis: Time to Sustained Withdrawal of Oxygen Supplementation, Plitidepsin 2.5 mg Vs Control Arm - Kaplan-Meier Plot (Intent-To-Treat Population)

• Include only patients in Plitidepsin 2.5 mg or Control Arm.

Figure 14.2.1.1.2 Post-hoc Analysis: Time to Sustained Withdrawal of Oxygen Supplementation, Plitidepsin 1.5 mg Vs Control Arm - Kaplan-Meier Plot (Intent-To-Treat Population)

• Include only patients in Plitidepsin 1.5 mg or Control Arm.

Figure 14.2.1.2.1 Post-hoc Analysis: Time to Sustained Withdrawal of Oxygen Supplementation - Subgroup Analysis - Forest Plot (Intent-To-Treat Population)

		Treatment A	Treatment B				
Subę	roup	Ν	Ν	HR (95% CI)		Hazard Ra	tio
Age	(years)						
-	<65	1077	1091	0.73 (0.55, 0.97)			
	≥65	862	846	0.79 (0.60, 1.03)		■	
Gen	der			, ,			
	Male	1293	1245	0.81 (0.64, 1.03)		-	
	Female	646	692	0.65 (0.46, 0.93)		⊨	
Race							
	White	1600	1619	0.77 (0.62, 0.98)		⊢	
	Black or African American	218	225	0.67 (0.39, 1.16)			
	Other	88	60	1.08 (0.35, 3.29)			 
Ethn	icity						
	Hispanic or Latino	75	72	0.58 (0.23, 1.46)			———————————————————————————————————————
	Not Hispanic	1852	1857	0.78 (0.63, 0.95)		⊢	
Body	MassIndex						
-	< 30	1123	1096	0.67 (0.52, 0.87)		⊢	
	≥ 30	810	835	0.91 (0.67, 1.24)		· · · · ·	
					0.25	0.5 1	1.5 2 3
					<	— Treatment A Better	Treatment B Better>

#### Statistical Analysis Plan Addendum and TFL Mock Shells Fortrea Study: 000000213894 Protocol Reference: APL-D-003-20

#### Programming notes (not part of the figure):

Type of figure	Forest Plot					
Figure Template ID Treatment display details	FG006 Display 2 tro	eatment groups per page	e. Plitidepsin 2.5mg vs	Control Arm on page 1 and Pl	itidepsin 1.5mg vs C	ontrol Arm on
X-axis label	< ( < (	Control Arm Better Control Arm Better	Plitidepsin 2.5mg Be Plitidepsin 1.5mg Be	tter> on page 1. tter> on page 2.		
X-axis Scale	0.33; 0.5; 0.	66; 1; 1.5; 2; 3.				
Y-axis label	Nil.					
Y-axis Scale	Major tick: 1 Display 2 tro	Nil>>, Minor tick: Nil. eatment groups per page	·.			
	Subgroup	Plitidepsin 2.5mg N	Control Arm N	HR [b] (95% CI)	Hazard Ratio	(on page 1)
Legend	Subgroup	Plitidepsin 1.5mg N	Control Arm N	HR [b] (95% CI)	Hazard Ratio	(on page 2)
Legend position	Тор					
Annotations Other notes	Include refer Display sub	rence line groups as following:				
	Al Cl Ga Pr Pa Se	ll patients narlson Comorbidity Inc 0 - 1 > 1 eographical Region Europe Rest of the World e-baseline Barthel index ≥ 90 < 90 stients included before a Protocol v.6 or befo Protocol v.7 x Female Male	lex c nd after amendment re			

Statistical Analysis Plan Addendum and TFL Mock Shells Fortrea Study: 000000213894 Protocol Reference: APL-D-003-20

> Age at study entry (years) 18 to 39 40 to 64  $\geq 65$ Race Asian Black White Other Ethnic group Hispanic or Latino Not Hispanic or Latino Site location: each study site with more than 1/6 out of the randomised patients (i.e. >33 randomised patients for the futility analysis and >101 randomised patients for the final analysis) will be considered as a group and the remaining study sites, i.e. those study sites with less than 1/6 out of the randomised patients will be pooled together as a one single group Site XXX Site XXX Other Sites Use of antiviral therapies or immunomodulatory drugs through the study Yes No Previous COVID-19 vaccination status Fully vaccinated Non-fully vaccinated No vaccinated Fully vaccinated + Non-fully vaccinated Anti-SARS-CoV-2 IgG Day 1 Non-positive Positive Pre-randomisation dexamethasone Yes No Total duration of corticoid therapy  $\leq 9$  days [9 11] days > 11 daysTotal cumulative dose of corticoid therapy (dexamethasone or equivalent) ≤ 60 mg

Final, Version 2.0, 12SEP2023

> 60 mgSARS-CoV-2 viral load (log10 copies/mL) at Day 1 before study drug administration < 4 [4 - 7] > 7Time between onset date of COVID-19 symptoms and initiation of study treatment  $\leq$  5 days 6 - 10 days >10 days Body mass index (kg/m2) at Screening < 30  $\geq$  30 Hypertension at Screening Yes No Myocardial infarction at Screening Yes No Congestive heart failure at Screening Yes No Peripheral vascular disease at Screening Yes No Cerebrovascular disease at Screening Yes No Dementia at Screening Yes No Chronic obstructive pulmonary disease at Screening Yes No Connective tissue disease at Screening Yes No Peptic ulcer disease at Screening Yes No

Final, Version 2.0, 12SEP2023

Page 39 of 43 ST-AD-008 version 06

Statistical Analysis Plan Addendum and TFL Mock Shells Fortrea Study: 000000213894 Protocol Reference: APL-D-003-20

> Liver disease at Screening None Mild Moderate or Severe Diabetes mellitus at Screening None or diet controlled Uncomplicated End-organ damage Hemiplegia at Screening Yes No Moderate or severe chronic kidney disease at Screening Yes No Solid tumor at Screening None Localized Metastatic Leukemia at Screening Yes No Lymphoma at Screening Yes No AIDS at Screening Yes No ISARIC-4C mortality score Low (0 - 3) Intermediate (4 - 8) High (9 - 14) Vey high ( $\geq 15$ ) ISARIC-4C deterioration probability (%)  $\leq 25$ (25 - 50] > 50 LDH at Baseline  $\leq$  ULN > ULN

Final, Version 2.0, 12SEP2023

Page 40 of 43 ST-AD-008 version 06

Statistical Analysis Plan Addendum and TFL Mock Shells Fortrea Study: 000000213894 Protocol Reference: APL-D-003-20

> CRP (mg/L) at Baseline  $\leq 100$ >100 D-dimer at Baseline  $\leq$  ULN > ULN Ferritin at Baseline  $\leq$  ULN >ULN Creatinine at Baseline  $\leq$  ULN >ULN IL-6 at Baseline  $\leq$  Median > Median IL-10 at Baseline  $\leq$  Median > Median IL-10 at Baseline  $\leq$  3.8 ng/L > 3.8 ng/LLymphocytes count decreased at Baseline Grade 0 Grade  $\geq 1$ Neutrophils/lymphocytes ratio at Baseline < 6  $\geq 6$ SARS-CoV-2 variant Alpha Beta Gamma Delta Eta Iota Kappa Lambda Mu <Any other potential new variant>

CONFIDENTIAL

Display the following footnotes:

HR = Hazard Ratio; CI = Confidence Interval; AIDS = Acquired Immunodeficiency Syndrome.
Charlson Comorbidity and pre-baseline Barthel Index as derived using the eCRF data.

#### **TMF File Note**

Sponsor Name:		Pharma Mar S.A.	Fortrea Study ID :	000000213894
Sponsor Protocol/CIP No.:		APL-D-003-20	Date (dd mmm yyyy)	03 Jul 2023
Investigator Name:	:	NA	Site No.:	NA
Artifact Name:		000000213894 Statistical Analysis Plan 21 Apr 2023	Artifact No:	CVD-TMF-7706943
		000000213894 Statistical Analysis Plan 24 Apr 2023		CVD-TMF-7706979
Topic :		Inaccurate document date in Statistical Analysis Plan v4.0 and SAP text filename and the TFL shells filename in the corresponding SAP v4.0 approval form		
Description: Artifac Due to version Artifac (Appro The SA form. T SAP te: TFL sh		t No: CVD-TMF-7706943 - 0000002 a mistake, the document date was not u 4.0. The correct document date is 21 A t No: CVD-TMF-7706979 - 0000002 val Form) P text filename and the TFL shells file he correct SAP text filename and the T t filename: Neptuno-A ells filename: Neptuno-A	13894 Statistical Analysis Pl updated in the footer of the Sta Apr 2023. 13894 Statistical Analysis Pl name are not correct in the co TFL shells filename are: PL-D-003-20_SAP Final v4.0 PL-D-003-20_SAP TFL Shel	an 21 Apr 2023 atistical Analysis Plan (SAP) text an 24 Apr 2023 prresponding SAP v4.0 approval 0_21Apr2023 ls Final v4.0_21Apr2023

# **Glossary of Abbreviations**

Abbreviation	Term
AE	adverse event
ALT	alanine aminotransferase
ANCOVA	analysis of covariance
AST	aspartate aminotransferase
ATC	anatomical therapeutic chemical
CI	confidence interval
CRP	C-reactive protein
COVID-19	coronavirus disease 2019
СРК	creatine phosphokinase
eCRF	electronic case report form
DMC	data monitoring committee
ECG	electrocardiogram
ECMO	extracorporeal membrane oxygenation
FAS	full analysis set
FiO 2	fraction of inspired oxygen
GGT	gamma-glutamyltransferase
ICU	intensive care unit
IDMC	independent data monitoring committee
Iq	immunoalobulin
TL	interleukin
IRT	interactive response technology
	intention-to-treat
IV	intravenous
	lactate dehydrogenase
1100	lower limit of quantification
	lowest level terms
LOCE	last observation carried forward
	limit of detection
15	
MedDRA	medical dictionary for regulatory activities
NIV	noninvasive ventilation
NIR	neutrophils/lymphocytes ratio
NRI	non-responder implication
NT-pro-BNP	N-terminal pro b-type natriuretic peptide
PO	oral administration
nO 2	partial pressure of oxygen
PP	per-protocol
PT	preferred term
aPCR	quantitative polymerase chain reaction
OTC	corrected OT interval
OTCF	Fridericia corrected OT interval
RNA	ribonucleic acid
SAF	serious adverse event
SAP	statistical analysis plan
SAR	serious adverse reactions
SARS-CoV-2	severe acute respiratory syndrome coronavirus 2
SD 50 2	standard deviation

#### Statistical Analysis Plan

Sponsor Name: Pharma Mar S.A. Sponsor Protocol ID: APL-D-003-20

Labcorp Drug Development Study ID: 000000213894

SE	standard error
SMQ	standardised MedDRA query
SOC	system organ class
SpO 2	saturation of oxygen
TEAE	treatment-emergent adverse event
TNFa	tumour necrosis factor alpha
TFLs	tables, figures and listings
ULN	upper limit of normal
WHO	World Health Organization

# **1. Source Documents**

The Statistical Analysis Plan (SAP) was written based on the following documentation:

Document	Date	Version
Protocol	29MAR2022	Final 7.0
Electronic case report form (eCRF)	27FEB2023	7.0
IDMC Charter	22APR2022	Final 3.0

## 2. Protocol Details

## **2.1 Study Objectives**

#### 2.1.1 Primary Objective

The primary objective of this study is to compare efficacy of plitidepsin 1.5 mg or 2.5 mg versus the control assessing the need of supplementary oxygen.

#### 2.1.2 Key Secondary Objective

The key secondary objective of this study is to compare efficacy of plitidepsin 1.5 mg and 2.5 mg versus the control assessing the time to sustained hospital discharge.

#### 2.1.3 Secondary Objectives

#### 2.1.3.1 Efficacy Secondary Objectives

The efficacy secondary objectives of this study are

- To compare efficacy of plitidepsin 1.5 mg or 2.5 mg versus the control assessing clinical status by the 11-category World Health Organization (WHO) Clinical Progression Scale.
- To compare efficacy of plitidepsin 1.5 mg or 2.5 mg versus the control in terms of the need of advanced oxygen support.
- To compare efficacy of plitidepsin 1.5 mg or 2.5 mg versus the control in terms of the need for intensive care support.

#### 2.1.3.2 Safety Secondary Objectives

The safety secondary objectives of this study are

- To compare safety/tolerability of plitidepsin 1.5 mg or 2.5 mg versus the control in terms of adverse events, adverse reactions and mortality.
- To compare safety/tolerability of plitidepsin 1.5 mg or 2.5 mg versus the control in terms of abnormal laboratory parameters.
- To compare safety/tolerability of plitidepsin 1.5 mg or 2.5 mg versus the control in terms of variations of vital signs.

• To compare safety/tolerability of plitidepsin 1.5 mg or 2.5 mg versus the control in terms of ECG variations.

#### 2.1.3.3 Other Secondary Objectives

The other efficacy secondary objectives of this study are

- To compare efficacy of plitidepsin 1.5 mg or 2.5 mg versus the control in terms of hospital readmission related to COVID-19.
- To compare efficacy of plitidepsin 1.5 mg or 2.5 mg versus the control in terms of clinical evolution.
- To compare efficacy of plitidepsin 1.5 mg or 2.5 mg versus the control in terms of the need of supplementary oxygen.
- To compare efficacy of plitidepsin 1.5 mg or 2.5 mg versus the control in terms of the need of intensification of respiratory or intensive care support.
- To compare efficacy of plitidepsin 1.5 mg or 2.5 mg versus the control in terms of the need of intensification of pharmacological therapies.
- To compare efficacy of plitidepsin 1.5 mg or 2.5 mg versus the control in terms of superinfections.
- To compare efficacy of plitidepsin 1.5 mg or 2.5 mg versus the control in terms of mortality.
- To compare efficacy of plitidepsin 1.5 mg or 2.5 mg versus the control in terms of the evolution of viral load.
- To compare efficacy of plitidepsin 1.5 mg or 2.5 mg versus the control in terms of the evolution of inflammatory markers.
- To compare efficacy of plitidepsin 1.5 mg or 2.5 mg versus the control in terms of the immune response against severe acute respiratory syndrome coronavirus 2 (SARS-CoV-2).
- To compare efficacy in the primary endpoint and describe safety/tolerability of pooled plitidepsin arms versus control.
- To compare efficacy in the primary endpoint and describe safety/tolerability between plitidepsin arms (1.5 versus 2.5 mg) in case both are significantly superior to the control.
- To explore the influence of risk factors or scores for clinical deterioration that were not individually included.
- To compare the results obtained before and after the change of the primary and key secondary endpoint (protocol v.6 versus v.7).

## 2.2 Overall Study Design

This is a randomised, multicentre, open-label, controlled Phase 3 study in which adults requiring hospital admission and oxygen supplementation for management of moderate COVID-19 infection will be randomised in 1:1:1 to:

- Plitidepsin 1.5 mg arm: Patients will receive plitidepsin 1.5 mg/day intravenous (IV) in addition to dexamethasone on days 1 to 3;
- Plitidepsin 2.5 mg arm: Patients will receive plitidepsin 2.5 mg/day IV in addition to dexamethasone on days 1 to 3;
- Control arm: Patients will receive dexamethasone IV on Days 1 to 3. Additionally, in accordance with local treatment guidelines, patients in this group may receive a regulatory-approved antiviral treatment.

The study allows up to a total cumulative dose of 60 mg of dexamethasone base (calculation of the total dose will also include corticosteroids administered within 72 hours before the start of the study treatment and dexamethasone administered as premedication).

Randomisation will be stratified for 3 factors:

- Geographical region (Europe vs. Rest of the World);
- Charlson Comorbidity Index (0-1 vs. >1); and
- Barthel Index (≥90 versus <90)

From treatment initiation on Day 1, patients will be followed in the hospital for at least 4 days and then through Day 31 ( $\pm$ 3 days) or resolution/stabilisation of treatment-related adverse events (AEs), treatment-emergent adverse events (TEAEs) of special interest, and serious adverse events (SAEs). Patients discharged from the hospital prior to Day 8 will return to an out-patient clinic for assessments on Days 8 ( $\pm$ 1 day), and 31 ( $\pm$ 3 days). On Day 15 ( $\pm$ 1 day), patients will be followed up in remote or on-site visit (Appendix 4).

An independent Data Monitoring Committee (IDMC) will oversee study conduct (safety and primary endpoint), including analysis of summary safety data as per the trial requirements.

The study is expected to randomise approximately 609 patients (203 in each arm) over a period of 20 months.

Patients will be considered to be on study from the signature of the informed consent form until the end of the follow-up period, that is, completion of the protocol-specified follow-up visit on Day 31 ( $\pm$ 3 days) or until resolution/ stabilisation of treatment-related AEs, TEAEs of special interest, and SAEs that occurred through Day 31, whichever is longer.

Additionally, a dedicated corrected QT interval (QTc) substudy will be performed in a subset of approximately 50 patients with electrocardiogram (ECG) collected over Days 1 to 3 using Holter monitors to assess treatment impact on QTc prolongation.

## 2.3 Sample Size and Power

A total sample size of 609 patients (203 in each arm) with 530 events necessary for the analysis of the primary endpoint has been calculated based on a 1-sided type I error rate of 1.25% ( $\alpha = 0.0125$ ) with at least 80% power ( $\beta = 0.2$ ) to detect target hazard ratio (HR) of 1.4 in the time to sustained withdrawal of supplementary oxygen, which means a decrease in the median time to the event from 8 days (control arm) to 5.7 days (plitidepsin). This sample size is adjusted for the multiple comparisons of each plitidepsin arm with control group by a Bonferroni adjustment, although other advanced methods for correction of multiplicity will be used for the main analysis that will increase the power of the tests. At the final analysis, if HR is 1.27 or greater, in favour of any plitidepsin arm, (equivalent to a decrease in the median time to sustained withdrawal of supplementary oxygen of 1.7 days or greater), then it is expected that the null hypothesis (ie, HR  $\leq$ 1) will be rejected.

A futility analysis for efficacy/safety will be performed when 33% of events (sustained withdrawal of supplementary oxygen) have been reached. The rho family of beta-spending functions (with  $\rho = 1.18$ ) will be used for the calculation of the stopping boundaries for futility in order to control type II error. The stopping boundaries for the futility analysis will be calculated with the actual number of events available in the Intent-To-Treat (ITT) population at that moment; if the number of events at the futility analysis is 116 events in a pair comparison, the beta spending corrected p-value to reject the alternative hypothesis should be higher or equal than 0.4199 and this p-value is associated with a  $HR \le 1.0382$ . At the futility analysis, once 33% of events of the planned 530 have been reached the conditional power will be calculated. As an example, if clinical trial design hypotheses are seen, a conditional power of 86.9% would be achieved for an interim test Z-statistic of 1.812 assuming the HR is 1.4 in favour of the plitidepsin arms (median time to the event of 5.7 for the plitidepsin arms compared with 8 days for the control arm) and a 1-sided analysis at the 1.25% significance level. If the recommendation of the IDMC is to discontinue one of the plitidepsin dosing arms at this futility analysis following the stopping rules, the study will continue from that point on a 1:1 randomisation fashion until the completion of the remaining treatment arms (203 patients per arm and 353 events of sustained withdrawal of supplementary oxygen in total necessary to perform the final analysis). The patients still ongoing in the dropped arm would continue to be followed-up as per protocol and a Bonferroni-adjusted type I error rate of 1.25% will be kept for the comparison of the primary endpoint between the remaining plitidepsin arm and the control arm.

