### 7.6.4 Subgroup Analysis

The primary and key secondary efficacy endpoint will be analysed using the ITT population by the following subgroups:

- Charlson Comorbidity index (as derived using the eCRF data): 0 1' or > 1'
- Geographical Region: Europe or Rest of the World
- Pre-baseline Barthel index:  $\geq 90'$  or  $\leq 90'$
- Patients included before and after amendment: 'Protocol v.6 or before' or 'Protocol v.7'

The same covariates used for the primary efficacy endpoint analysis will be used for the subgroup analyses except that for the Charlson Comorbidity index subgroup analysis, the randomisation stratum of Charlson Comorbidity index will not be included as a covariate; for the Geographical Region subgroup analysis, the randomisation stratum of Geographical Region will not be included as a covariate; and for the pre-baseline Barthel index subgroup analysis, the randomisation stratum of pre-baseline Barthel index will not be included as a covariate.

Additionally, the primary efficacy endpoint will be analysed by the following subgroups:

- Sex: female or male
- Age at study entry: '18 to 39', '40 to 64' or ' $\geq$  65 years'
- Race: Asian, black, white or other
- Ethnic group: 'Hispanic or Latino' or 'Not Hispanic or Latino'

- Site location: each study site with more than 1/6 out of the randomised patients (ie, >33 randomised patients for the futility analysis and >101 randomised patients for the final analysis) will be considered as a group and the remaining study sites, ie, those study sites with less than 1/6 out of the randomised patients will be pooled together as a one single group.
- Use of antiviral therapies or immunomodulatory drugs through the study: Yes or No
- Previous COVID-19 vaccination status: 'Fully vaccinated', 'Non-fully vaccinated', 'No vaccinated', or 'Fully vaccinated + Non-fully vaccinated'
- Anti-SARS-CoV-2 IgG at Day 1: 'Non-positive' or 'Positive'
- Pre-randomisation dexamethasone: Yes or No
- Total duration of corticoid therapy: `< 9 days', `[9 11] days' or `> 11 days'
- Total cumulative dose of corticoid therapy (dexamethasone or equivalent): `≤ 60 mg' or `> 60 mg'
- SARS-CoV-2 viral load (log10 copies/mL) at Day 1 before study drug administration: '< 4', `[4 - 7]' or `> 7'
- Time between onset date of COVID-19 symptoms and initiation of study treatment: `≤ 5 days', `6 - 10 days' or `> 10 days'
- Body mass index (kg/m^2) at Screening: < 30 or  $\geq$  30 (Obesity)

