# 8. Changes in Planned Analysis

Despite wording in Protocol that WHO score 0 requires a test with RNA undetected (which would be achieved with a PCR or similar test), as scarce cases have been reported, Pharma Mar is accepting negative antigen tests (which is a protein detection test, and not RNA detection test) qualifying for score of 0.

Recruitment was stopped due to slow recruitment before reaching the 33% of events by Pharma Mar decision and futility analysis was cancelled.

An exploratory analysis of the comparison of the primary efficacy endpoint between each dose of plitidepsin versus control arm receiving and not receiving the antiviral control arm, ie, the regulatory-approved antiviral for those patients randomised to the control arm (remdesivir or favipiravir), will be performed.

CONFIDENTIAL

An exploratory analysis of the prior primary efficacy endpoint based on protocol amendment v6 will be performed at the final analysis time due to some regulatory agencies request.

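### SAP v4.0 section 2.3 still gives HR 1.27 as enough for rejection at the final analysis, although section 8 records that recruitment stopped before 33% of events

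*SAP*

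**What the plan says.** Section 2.3 sets out the design: "A total sample size of 609 patients (203 in each arm) with 530 events necessary for the analysis of the primary endpoint", a sample size that "has been calculated based on a 1-sided type I error rate of 1.25"%, "with at least 80% power" "to detect target hazard ratio (HR) of 1.4 in the time to sustained withdrawal of supplementary oxygen". It then moves from planning to interpretation: "At the final analysis, if HR is 1.27 or greater, in favour of any plitidepsin arm", which it equates with a median gain of 1.7 days or more, the null is expected to be rejected. Section 2.2 still looks forward: "The study is expected to randomise approximately 609 patients (203 in each arm) over a period of 20 months".

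Section 8 of the same version states: "Recruitment was stopped due to slow recruitment before reaching the 33% of events by Pharma Mar decision and futility analysis was cancelled". Section 7.8 puts the 33% mark at 175 events, and sections 2.3 and 7.8 put it at 116 events in one pairwise comparison. No section gives the number actually randomised or the number of events, or restates the critical HR or power.

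Section 7.6.4 makes each site with more than one sixth of the randomised patients its own subgroup, and glosses this as ">33 randomised patients for the futility analysis and >101 randomised patients for the final analysis". Section 7.7.7, the forest-plot shell (Figure 14.2.1.2) and its post-hoc repeat in the addendum (Figure 14.2.1.2.1) carry the same numbers.

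**The concern.** The HR 1.27 sentence is about the final analysis, not only about planning, and the same document shows that the event count behind it was not going to be reached by the planned route. Version 4.0 was written with the stop known: it cancels the futility analysis and adds a bootstrap to the original 203 per arm because recruitment had ended. It is dated 21 April 2023, five days before database lock.

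These figures tell a reader what a result means. Taken at face value, an observed HR of 1.3 would look sufficient, and a non-significant result would look like an adequately powered test of HR 1.4. On any event count near the 33% mark, neither holds. The bootstrap does not fill the gap, because it describes results at 203 per arm and not the precision attained.

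The site cut-off has the same fault on a smaller scale: a number derived from 609 patients sits beside a rule defined on the patients randomised.

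**Working it through.** **Inputs.** Section 2.3: 1-sided alpha 0.0125 (z = 2.2414), target HR 1.4, 530 events and 609 patients in three equal arms, 353 events for one pair, control median 8 days. Sections 2.3 and 7.8: 33% of events = 175 in all, 116 per pair. Section 7.6.1: Hochberg, with a 2-sided 0.05 step (z = 1.9600) if both doses pass and 2-sided 0.025 otherwise.

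**Formulas** (Schoenfeld, 1:1, d = events per pair): critical HR = exp(2z/√d); power = Φ(ln(1.4)·√d/2 − z).

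**The plan's own figures reproduce.**
- 530 × 2/3 = 353.3 events per pair.
- Critical HR = exp(2 × 2.2414/√353) = 1.269, and 8 − 8/1.269 = 1.70 days.
- Power = Φ(0.3365 × 18.79/2 − 2.2414) = Φ(0.92) = 82.1%. With the futility rule (p ≥ 0.4199 at 116 of 353 events) simulation gives 80.1%, so at least 80% is right for the design.
- The interim figures also reproduce: HR 1.038 at the futility bound, Z = 1.812 for HR 1.4, conditional power 86.9%.

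**Where HR 1.27 is valid.** Solving for d:
- at 1-sided 1.25%: d = (2 × 2.2414/ln 1.27)² ≈ 352;
- at Hochberg's lenient step: d = (2 × 1.96/ln 1.27)² ≈ 269.

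Even the lenient step needs more than twice the 116 events per pair at the 33% mark.

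**At the 33% mark.** 175 × 2/3 = 116.7, about 117 per pair with events split evenly over the arms.
- Critical HR = exp(4.4828/10.82) = 1.514. The control median of 8 days would have to fall to 8/1.514 = 5.3 days, a gain of 2.7 days.
- Power at HR 1.4 = Φ(1.820 − 2.241) = 33.7%.
- Hochberg by simulation, both true HRs 1.4, correlation 0.5 from the shared control: 39% per dose, 50% for at least one dose.

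**Range**, because the final count is not stated:

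| Events per pair | Events in all (× 3/2) | Critical HR, 1-sided 1.25% | Power at HR 1.4, 1-sided 1.25% | Critical HR, 2-sided 0.05 (both doses pass) |
|---|---|---|---|---|
| 80 | 120 | 1.651 | 23% | 1.550 |
| 100 | 150 | 1.566 | 29% | 1.480 |
| 117 | 175 | 1.514 | 34% | 1.437 |
| 140 | 210 | 1.461 | 40% | 1.393 |
| 175 | 262 | 1.403 | 49% | 1.345 |

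Every row has a threshold above 1.27 and power well below 80%.

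**Site cut-off.** 609/6 = 101.5, hence >101. At the planned event fraction, 530/609 = 0.87, 175 events correspond to about 201 patients, and 201/6 = 33.5, which matches the SAP's >33. If the number randomised ended near 200 (an assumption), more than one sixth would mean more than 33 patients, while >101 would require one site to hold about half the trial.

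**The case against.** The strongest reply is that nothing in section 2.3 is miscalculated. Every design figure reproduces. The power sentence is worded as a calculation already made, in a chapter that restates protocol details. HR 1.27 is an expectation and not a decision rule: the decision rests on the stratified log-rank p-values under Hochberg. The stop is disclosed in section 8, and hazard ratios come with 95% confidence intervals that show directly whether 1.4 is excluded. All of this stands, and it limits the point to stated figures that no longer describe the analysis. It does not rescue the HR 1.27 sentence, which speaks of the final analysis and is not labelled as superseded.

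Four stronger readings are tempting, and the document does not support them.
- A reader might infer that the trial's true power is 34% and its true threshold 1.51. No final event count is given. The count at the stop could be well below 175, or patients still in follow-up to Day 31 could take the total above it. Both numbers also use the Bonferroni level, whereas the planned test is Hochberg.
- A reader might infer that the 80% power statement is false. It is correct for the original design and lacks only a label.
- A reader might infer that the planned site subgroup would be empty, with every site pooled. The governing rule is one sixth of those randomised and >101 is its gloss. The outcome depends on which is programmed and on site sizes that are not stated.
- A reader might connect this with the post-hoc tables for site ES40. The addendum gives no reason for choosing that site.

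**Conclusion.** The point holds as an out-of-date statement about the final analysis. HR 1.27 and 1.7 days are right at about 353 events per pair and wrong at any count near the recorded stop. If the analysis had about 117 events per pair, the critical HR would be about 1.51 (1.44 if both doses pass at the lenient step), and power for HR 1.4 would be about 34% at the Bonferroni level. From 80 to 175 events per pair the figures run from 23% and 1.65 to 49% and 1.40. These rest on proportional hazards, an even split of events across arms and the Schoenfeld approximation, which reproduces the SAP's own numbers. The Hochberg figures also assume that both true HRs are 1.4.

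The primary test and its type I error are not affected; what is affected is how a positive or null result would be read. The fixed >101 conflicts with the one-sixth rule once the number randomised falls well short of 609.

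**What to change.** In sections 2.3 and 8, state the actual numbers randomised and events. Label 609 patients, 530 events, 80% power, HR 1.27 and 1.7 days as original design, and bring the expected-enrolment sentence in 2.2 into line. Give the critical HR and the power at HR 1.4 for the actual events, at both Hochberg steps. Add that a non-significant result does not by itself exclude HR 1.4.

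In sections 7.6.4 and 7.7.7 and the forest-plot shells, including the addendum's repeat, delete the fixed >101 and keep the rule as more than one sixth of the patients actually randomised.

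The cost is a text change and a short recalculation. No test or population changes; the stated figures become less favourable.
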